## Protocol Synopsis

Study title	Investigating the mechanisms of short- and long-term responses to IL-23 inhibition using Tildrakizumab in moderate to severe plaque psoriasis using high-definition multiomics
Hypothesis	Define the mechanisms underlying the short- and the long-lasting effects of IL-23 targeting in plaque PsO, by characterizing the longitudinal effects of IL-23 inhibition on the ratio of Trm/Treg cells in the skin of moderate to severe plaque PsO patients.
Objectives	HDST (Visium HD) and HDSP (MICS) are used to characterize the early (2 weeks) and late (16 weeks) molecular effects of treatment with tildrakizumab on the skin of three patients with moderate to severe plaque psoriasis. Non-lesional and lesional skin samples taken at the start of treatment with tildrakizumab will be used, as well as healed skin adjacent to the original sampling sites at week 2 and week 16 after the start of treatment with tildrakizumab. The same samples will be examined using Visium HD and the MACSima imaging system.
Study design	This is a retrospective, exploratory study using material from our existing biobank (Excellence cluster, 'Clinical Demonstrator 1') in patients with moderate-to-severe plaque psoriasis who received Tildrakizumab treatment.
Sample size	3 patients
Study site location	The study will be conducted at the Institute for Inflammation Medicine at the University of Lübeck, Lübeck, Germany

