Targeted therapies like ustekinumab, which inhibit the IL-12/23p40 subunit, have proven effective in treating plaque PsO. Furthermore, evidence from tissue expression and genetic studies indicates that the therapeutic impact of these agents is largely due to their ability to block IL-23, rather than IL-12 (10), underscoring the significance of the IL-23 pathway. Furthermore, a head to head comparison suggests that IL-23p19 inhibitors like guselkumab and risankizumab offer superior efficacy over TNF inhibitors such as adalimumab (11) and IL-17A inhibitors like secukinumab (12). Nevertheless, IL-17A inhibitors, including secukinumab and ixekizumab, exhibit a faster onset of action compared to IL-23p19 inhibitors in the treatment of plaque PsO (13).

Tildrakizumab is a high-affinity, humanized, IgG1/k monoclonal antibody that selectively binds to the (IL)-23p19 subunit but does not bind to human IL-12 or the IL-12/23p40 subunit (18). Importantly, treatment effects that were achieved over the first 16 weeks of treatment were maintained through 52 weeks of treatment with doses of 100 and 200 mg Tildrakizumab (19). Upon cessation of treatment, the rate of relapse was low during a 20-week nontreatment period

(19), suggesting that Tildrakizumab might have beneficial effect in clearing Trm cells and expanding Treg cells in the skin in plaque PsO patients.

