Global spatial transcriptomics (ST) revolutionized the study of drug effects within tissues by charting the spatial organization of cells while preserving their native cellular context (20). Furthermore, it permitted studying cell-cell interactions and eliminated the biases associated with cell dissociation and recovery, especially in extracellular matrix-rich tissues, like skin (21). Though conventional spatial profiling methods captured spatial data in intact tissues, they often relied on pre-selected markers and lacked adequate resolution (22). The recently established cutting edge high-definition spatial transcriptomics (HDST) approach (10x Genomics) overcomes these limitations by combining spatial barcoding with high-resolution RNA sequencing (23). Using this novel technology, we can now map precise localization of gene expression at every 2  $\mu$ m achieving a single-cell resolution (22,23). In addition to HDST, spatial proteomics methods such as MICS also known as MACSima Imaging Cyclic Staining technology (Miltenyi Biotec) enabled the immunofluorescent imaging of hundreds of protein targets across a single specimen at subcellular resolution, and offered new insights into cellular complexity of the skin in response to treatment (24,25). By integrating data from these state-of-the-art technologies, we aim to study the short (2 weeks after initiation of treatment) and the long-term effects (16 weeks after initiation of treatment) of Tildrakizumab treatment on the cellular composition and activation in the skin of plaque PSO patients, especially of Trm and Treg cells.

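### Does the aim of explaining long-lasting effects ask more than samples at baseline, week 2 and week 16 can give?

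*Protocol*

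**What the plan says.** The Hypothesis row of the Protocol Synopsis states the aim as "Define the mechanisms underlying the short- and the long-lasting effects of IL-23 targeting in plaque PsO". The rest of that sentence says how: by characterising changes over time in the ratio of Trm to Treg cells in the skin.

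The Objectives row gives the scope as to "characterize the early (2 weeks) and late (16 weeks) molecular effects of treatment with tildrakizumab" in three patients. The samples are lesional and non-lesional skin from the start of treatment, followed by "healed skin adjacent to the original sampling sites at week 2 and week 16 after the start of treatment with tildrakizumab". The Study design row reads "This is a retrospective, exploratory study using material from our existing biobank".

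Section 1 (Background) reports from a cited trial that "treatment effects that were achieved over the first 16 weeks of treatment were maintained through 52 weeks of treatment" and then "Upon cessation of treatment, the rate of relapse was low during a 20-week nontreatment period", "suggesting that Tildrakizumab might have beneficial effect in clearing Trm cells and expanding Treg cells in the skin". The same section later names the study's own late horizon as "the long-term effects (16 weeks after initiation of treatment". Section 2 (Study Purpose) speaks of short- and long-term effects during treatment. Section 3 (Study Methodology) repeats the early and late time points at 2 and 16 weeks.

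**The concern.** Two words in the Hypothesis row seem to claim more than the material can support.

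The first is 'long-lasting'. As shown, section 1 leads to the Trm/Treg idea from evidence of persistence: maintained response to week 52 and little relapse over 20 weeks off drug. A reader coming from that paragraph could take 'long-lasting' to mean an effect that outlives week 16, or outlives treatment. A lower Trm/Treg ratio at week 16 on drug fits two explanations: lasting clearance of Trm cells, or suppression that reverses once the drug is withdrawn. On-treatment samples alone cannot tell these apart, and more patients would not help.

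The second is 'define', used in both the Hypothesis row and section 2. The design row calls the study exploratory, there are three patients, and no untreated comparator is described. Such data support description and the forming of hypotheses.

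What would be at stake is interpretation: a week-16 finding might be reported as a mechanism of durability.

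**Working it through.** The protocol states no power, significance level or effect size, and the question needs none. The check compares sampling times with the stated aim, then compares the protocol's time words with each other.

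**Inputs.** Three patients (Synopsis, Sample size). Time points at treatment start, week 2 and week 16 (Synopsis, Objectives). Effects studied during treatment (section 2). Cited-trial horizon of 52 weeks on drug and 20 weeks off drug (section 1).

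**What the samples cover**, assuming each patient contributes at every time point:

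- All patient-visits: 3 × 3 = 9.
- After treatment start: 3 × 2 = 6, all on treatment. This last point is inferred from section 2; it is not written beside the week-16 sample.
- After week 16: 0. After stopping treatment: 0.
- Span over which persistence can be seen: 16 − 2 = 14 weeks, under continued exposure.

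**Against the cited trial's horizon.** 16/52 = 31% of the on-treatment period, and 0 of the 20 off-treatment weeks. If the two periods ran one after the other (an assumption), 16/(52 + 20) = 16/72 = 22%. So if 'long-lasting' meant that horizon, the samples would fall well short.

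**Whether it does mean that horizon.** The time words side by side:

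| Place | Words for the two horizons |
|---|---|
| Synopsis, study title | short- and long-term |
| Synopsis, Hypothesis | short- and long-lasting |
| Synopsis, Objectives | early (2 weeks), late (16 weeks) |
| Section 1, last paragraph | short (2 weeks), long-term (16 weeks) |
| Section 2 | short- and long-term |
| Section 3 | early (2 weeks), late (16 weeks) |

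Five of the six places use a long-term or late label. Three of those five tie it to 16 weeks in figures, and none ties it to anything later. 'Long-lasting' appears once, in the position that 'long-term' or 'late' fills everywhere else. The consistent reading is that it names the same week-16 horizon, and on that reading the samples match the aim.

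**Whether any stated objective needs later data.** None mentions relapse, withdrawal, reversibility, or telling clearance from suppression. The 52-week and 20-week figures are background from another trial, and the inference drawn from them is hedged.

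**Whether 'define' misleads.** The same sentence goes on to say that this will be done by characterising changes over time. The same table gives the exploratory design and the three patients. The document makes no confirmatory claim.

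**The case for a change.** The best case for acting runs as follows. The rationale for looking at Trm and Treg cells, as shown, is durability. The Hypothesis row echoes it with a word that the protocol nowhere defines; section 1 fixes the meaning of 'long-term', which is a different word. If 'long-lasting' means durability, the samples cannot deliver the aim. If it means week 16, it is the one term out of line. Either way the same small edit would cure it, at almost no cost, and a sentence limiting claims about persistence would guard against over-reading. The hypothesis is protocol content, so the matter cannot be left to an analysis plan.

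Part of this stands. Persistence beyond week 16 or off drug cannot be shown from the samples listed, and the word is looser than its neighbours.

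Three things weaken the rest. First, a week-2 change that is still there at week 16 can be described, so it is too strong to say that nothing about lasting change can be learned. Second, the Synopsis lists the samples to be used, not everything the biobank holds. Third, the rationale shown may be incomplete: citations in section 1 pass from 13 to 18, while references 14 to 17 concern tissue-resident memory and regulatory T cells. Durability therefore cannot be taken as the whole reason for the Trm/Treg focus. The suggested limiting sentence would rule out an inference that the protocol never says it will draw from its own data.

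**Conclusion.** No change to the plan is needed. The sampling limit is real: 6 patient-visits after baseline, all taken to be on treatment, and none later. But the protocol's own usage places its late horizon at 16 weeks, and the samples reach that horizon. What remains is a single loose synonym, plus an ambitious verb in an aim that the same table qualifies as exploratory. Replacing either would be harmless tidying; it would leave every sample, assay, comparison and result as it is.

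This conclusion rests on reading 'long-lasting' as the week-16 effect, as the rest of the document supports, and on section 2 for the samples being on treatment. It would be different if the protocol had an objective on relapse, withdrawal or maintenance beyond week 16. Colleagues reading the eventual report should simply take a week-16 Trm/Treg ratio as an on-treatment description.

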## **2. Study Purpose**

This study aims to define the mechanisms underlying both short- and long-term effects of IL-23 inhibition in patients with moderate-to-severe plaque psoriasis during treatment with Tildrakizumab. Specifically, the study will investigate longitudinal changes in the ratio of tissue-resident memory T cells (Trm) to regulatory T cells (Treg) in lesional, non-lesional, and resolved skin. In addition, the study will assess spatial and temporal alterations in IL-23 source and target cells using high-definition spatial transcriptomics (Visium HD) and high-dimensional spatial proteomics (MACSima MICS).

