## **3. Study Methodology**

The study will use HDST (Visium HD) and HDSP (MACSima Imaging Cyclic Staining – MICS) to analyze early (2 weeks) and late (16 weeks) molecular effects of Tildrakizumab treatment in the skin of three moderate-to-severe plaque psoriasis patients using previously collected

biopsies from our existing biobank. Sections will be subjected to spatial transcriptomic analysis using Visium HD and multiplex imaging with the MACSima system.

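### Follow-up skin is taken beside the baseline biopsy sites, so time on drug runs in step with the age of a neighbouring biopsy site, and week-2 and week-16 changes may be confounded by local repair

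*Protocol*

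**What the plan says.** The Objectives in the Protocol Synopsis define the samples. For baseline: "Non-lesional and lesional skin samples taken at the start of treatment with tildrakizumab will be used". For follow-up, the plan uses healed skin "adjacent to the original sampling sites at week 2 and week 16 after the start of treatment". The stated goal is to "characterize the early (2 weeks) and late (16 weeks) molecular effects of treatment with tildrakizumab", and Section 3 (Study Methodology) repeats it: the platforms are to analyse "early (2 weeks) and late (16 weeks) molecular effects of Tildrakizumab treatment in the skin".

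The outcomes are local skin measures. Section 2 (Study Purpose) names "longitudinal changes in the ratio of tissue-resident memory T cells (Trm) to regulatory T cells (Treg" and lists lesional, non-lesional and resolved skin. Section 1 (Background) describes effects "on the cellular composition and activation in the skin of plaque PSO patients, especially of Trm and Treg cells".

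The synopsis states the setting: "This is a retrospective, exploratory study using material from our existing biobank". There are three patients, all treated. The protocol gives no distance between follow-up and baseline biopsies. It describes no follow-up sample from a site away from earlier biopsies, no untreated comparator, and no step to identify repair tissue.

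**The concern.** A before-and-after comparison reads the time difference as the treatment effect. Here a second thing changes at the same time: each follow-up sample has an earlier biopsy site beside it, and that site ages exactly as the treatment does. The baseline samples are the biopsies that created those sites.

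The outcomes are immune-cell composition and activation in skin, which local tissue repair could plausibly move. If it does so at the sampled location, two comparisons are affected: the change from baseline to week 2, and the early-versus-late difference, which sets skin beside a recent biopsy against skin beside an old one. All patients share the layout, so agreement among the three would be no safeguard. A repair signal could be reported as an early effect of IL-23 inhibition. A fall in the Trm/Treg ratio would be especially easy to misread, because Section 1 anticipates a benefit through fewer Trm and more Treg cells.

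**Working it through.** The protocol gives no power, effect size or variance behind its three patients, so there is no figure of its own to reproduce. The check concerns the layout.

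**Inputs from the Protocol Synopsis**
- Baseline: lesional and non-lesional skin at treatment start.
- Follow-up: weeks 2 and 16, adjacent to the baseline sites.
- Patients: 3.

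**Step 1: age of the neighbouring site.** Baseline biopsies are taken at treatment start, so the age of the neighbouring site equals weeks since treatment start.

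| Sample | Weeks on drug | Age of neighbouring baseline biopsy site |
|---|---|---|
| Baseline | 0 | none described |
| Week 2 | 2 | about 2 weeks |
| Week 16 | 16 | about 16 weeks |

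If the week-16 sample also lies near the week-2 biopsy, that second site is about 16 − 2 = 14 weeks old. The protocol does not say whether it does.

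**Step 2: can the two be separated at sample level?** Take a design matrix with 8 columns: three patient effects, lesional site, week 2, week 16, neighbouring site aged 2 weeks, and neighbouring site aged 16 weeks.

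| Layout | Rows | Rank | Correlation, week-2 column with 2-week-site column |
|---|---|---|---|
| One follow-up site per patient | 4 × 3 = 12 | 6 of 8 | 1.00 |
| Follow-up beside both baseline sites | 6 × 3 = 18 | 6 of 8 | 1.00 |
| Illustration: first layout plus remote follow-up samples | 6 × 3 = 18 | 8 of 8 | 0.63 |

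In both layouts compatible with the protocol the site-age columns duplicate the week columns. More patients sampled the same way would not change this. The result follows directly from how the layout is coded. It shows that an adjacent-site effect, if there is one, could not be separated from the time effect at sample level. It does not show that such an effect exists.

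**Step 3: what an effect would do to the ratio.** The documents give no effect size, so the inputs here are assumptions. If repair multiplies local Treg by (1 + f) and leaves Trm unchanged, the Trm/Treg ratio is multiplied by 1/(1 + f).

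| Assumed f | Ratio if Treg rises | Ratio if Trm rises instead |
|---|---|---|
| 10% | 1/1.10 = 0.91 (−9%) | 1.10 (+10%) |
| 25% | 1/1.25 = 0.80 (−20%) | 1.25 (+25%) |
| 50% | 1/1.50 = 0.67 (−33%) | 1.50 (+50%) |

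Zero is also possible, if the samples lie beyond the repair zone. Neither the direction nor the size can be taken from the protocol.

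**The case against.** **The follow-up skin is called healed.** This may mean resolved plaque, in line with the resolved skin of Section 2, or it may describe the biopsy area. The ambiguity stands, but adjacency to the earlier site holds under either reading.

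**Adjacent sampling has a purpose.** It keeps anatomical location and plaque constant, and remote sites would add between-site variation. This is right. The samples are also already collected, so the point is not an argument for different sampling.

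**Any factor that moves with time is inseparable in a single-arm series.** This is true of season or natural course as well. What distinguishes the biopsy site is that it is local and that both platforms keep position within the section, so part of the problem can be examined in the data at hand.

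**The study is exploratory, and analysis detail may sit in an analysis plan not shown here.** Both limit the weight of the point. The sampling location and the attribution to tildrakizumab are, however, fixed in the protocol itself.

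Three stronger readings are tempting, and the documents do not support them:
- A reader might infer that the week-2 effect *is* a wound effect, or is uninterpretable. Without a distance, a biopsy size or any evidence of a repair effect, only possible confounding can be claimed.
- A reader might count three of three week-2 samples beside a biopsy wound against none of six baseline samples. The protocol does not give the number of follow-up sites per patient, and its plural for the sampling sites would allow six week-2 samples. That the baseline sites had no earlier biopsy nearby is inferred, not stated.
- A reader might infer that a difference remaining outside visible scar must be due to the drug. Repair signals need not stop at a histological border, and there is no untreated comparator.

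**Conclusion.** The concern holds as possible confounding. Time on drug coincides with the age of a neighbouring biopsy site, about 2 and about 16 weeks, and nothing described in the protocol separates the two, yet the Objectives and Section 3 call the differences effects of tildrakizumab. This rests on the stated sampling locations and on baseline biopsies coinciding with treatment start. It does not depend on the number of patients.

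The size is unknown. It depends on how far the samples lie from the earlier biopsy, on the biopsy size, and on whether repair moves Trm or Treg there at all. The 9% to 33% fall, or 10% to 50% rise, holds only under the assumed inputs, and the true effect may be negligible. Active repair is presumably less of a concern at 16 weeks than at 2. This is a cheap improvement to analysis and wording, not a defect that invalidates the study.

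**What to change.** Use the existing samples only.

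1. From the biobank record, tabulate for each follow-up sample the distance and the days from the nearest earlier biopsy. If the distances are large, this alone may settle the matter.
2. Mark scar or repair tissue on all sections, baseline included, by the same criteria, before any cell counting and without reference to time point where feasible.
3. Report the Trm/Treg ratio and the expression contrasts with and without the marked tissue.
4. In the Objectives and Section 3, describe week-2 and week-16 results as changes after treatment start in skin adjacent to an earlier biopsy. Do not attribute to tildrakizumab any difference that disappears when repair tissue is excluded. State that differences which persist are consistent with a drug effect but do not prove one, since there is no untreated comparator.

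The cost is some annotation work, one sensitivity analysis and a change of wording. Excluding tissue leaves fewer cells per section and a somewhat less even match of tissue area between time points, which is why both versions should be shown. No new biopsy or patient is needed.

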## **List of abbreviations**

HDST	high-definition spatial transcriptomics
mDCs	myeloid dendritic cells
pDCs	plasmacytoid dendritic cells
PsO	Psoriasis
UKSH	University Medical Center Schleswig-Holstein

## 1. Background

Psoriasis (PsO), a chronic inflammatory skin disease that affects up to 2-3% of the western population (1) and ~125 million people worldwide (2). It is marked by the presence of red, scaly plaques that are commonly seen in its plaque-type form that accounts for over 80% of all PsO cases (3). Its development is driven by a complex interplay of genetic and environmental factors, and involves both keratinocytes, and innate and adaptive immune cells (4). Early activation of keratinocytes, leads to activation of plasmacytoid dendritic cells (pDCs), that in turn release IFN- $\alpha$  and stimulate myeloid dendritic cells (mDCs) to produce interleukin (IL)-23 (5). The IL-23 cytokine, composed of the IL-12/23p40 subunit, which is shared with IL-12, and the IL-23p19 subunit, is crucial in sustaining the inflammatory response in plaque PsO by activating distinct subsets of IL-17-producing lymphoid cells such as CD4+ helper T cells (Th17), cytotoxic CD8+ T cells (Tc17),  $\gamma\delta$  T cells, and innate lymphoid cells (ILC3) (6). In the presence of IL-23, these IL-17 producing cells expand clonally and secrete large amounts of IL-17, in particular, the IL-17A and IL-17F cytokines that drive the key pathological features in plaque PsO (7). Elevated IL-17 levels promote keratinocyte proliferation, angiogenesis, upregulation of adhesion molecules on endothelial cells, and immune cell recruitment into the skin. This, in turn, leads to a feedforward inflammatory loop, amplifying keratinocyte hyperproliferation and sustaining the disease pathology (8). While mDCs are the main producers of IL-23, other cell types, such as, macrophages, also contribute to IL-23 production (9). These additional sources may play a role in the pathogenesis and persistence of psoriatic lesions, further highlighting the complexity of PsO-related inflammation.

Targeted therapies like ustekinumab, which inhibit the IL-12/23p40 subunit, have proven effective in treating plaque PsO. Furthermore, evidence from tissue expression and genetic studies indicates that the therapeutic impact of these agents is largely due to their ability to block IL-23, rather than IL-12 (10), underscoring the significance of the IL-23 pathway. Furthermore, a head to head comparison suggests that IL-23p19 inhibitors like guselkumab and risankizumab offer superior efficacy over TNF inhibitors such as adalimumab (11) and IL-17A inhibitors like secukinumab (12). Nevertheless, IL-17A inhibitors, including secukinumab and ixekizumab, exhibit a faster onset of action compared to IL-23p19 inhibitors in the treatment of plaque PsO (13).

Tildrakizumab is a high-affinity, humanized, IgG1/k monoclonal antibody that selectively binds to the (IL)-23p19 subunit but does not bind to human IL-12 or the IL-12/23p40 subunit (18). Importantly, treatment effects that were achieved over the first 16 weeks of treatment were maintained through 52 weeks of treatment with doses of 100 and 200 mg Tildrakizumab (19). Upon cessation of treatment, the rate of relapse was low during a 20-week nontreatment period

(19), suggesting that Tildrakizumab might have beneficial effect in clearing Trm cells and expanding Treg cells in the skin in plaque PsO patients.

Global spatial transcriptomics (ST) revolutionized the study of drug effects within tissues by charting the spatial organization of cells while preserving their native cellular context (20). Furthermore, it permitted studying cell-cell interactions and eliminated the biases associated with cell dissociation and recovery, especially in extracellular matrix-rich tissues, like skin (21). Though conventional spatial profiling methods captured spatial data in intact tissues, they often relied on pre-selected markers and lacked adequate resolution (22). The recently established cutting edge high-definition spatial transcriptomics (HDST) approach (10x Genomics) overcomes these limitations by combining spatial barcoding with high-resolution RNA sequencing (23). Using this novel technology, we can now map precise localization of gene expression at every 2  $\mu$ m achieving a single-cell resolution (22,23). In addition to HDST, spatial proteomics methods such as MICS also known as MACSima Imaging Cyclic Staining technology (Miltenyi Biotec) enabled the immunofluorescent imaging of hundreds of protein targets across a single specimen at subcellular resolution, and offered new insights into cellular complexity of the skin in response to treatment (24,25). By integrating data from these state-of-the-art technologies, we aim to study the short (2 weeks after initiation of treatment) and the long-term effects (16 weeks after initiation of treatment) of Tildrakizumab treatment on the cellular composition and activation in the skin of plaque PSO patients, especially of Trm and Treg cells.

